2.3 Tranexemic Acid in orthopaedic surgery

2.3.1 Tranexemic acid in spine surgeries

Both intravenous and topical Tranexemic acid have been employed in spine surgery. Meta-analysis data analysis showed TXA reduced intraoperative, postoperative, and total blood loss by averages of 219, 119 (-141, - 98; p<00001), and 319 mL, respectively. 33% reductions in blood transfusion (0.54, 0.83; p<000001) and no apparent increase in Deep Venous Thrombosis (DVT) nor myocardial infarctions.(27)

Pradeep et al used intravenous TXA 10mg/kg versus placebo preoperatively in stabilization surgeries noted a significant decrease in intraoperative blood loss 1042ml in cases and 1149 in controls (p<0.033), thereby decreasing intraoperative transfusions however they noted that there was no major impact on postoperative blood loss 318ml in cases and 354 in controls. In their study they did not observe any thromboembolic events nor adverse effects.(15)

Ho Yong Choi et al also used intravenous loading dose ofTXA 10mg/kg in spinal deformity correction and noted use ofTXA can provide beneficial effects not only on reducing surgical bleeding (case 841 vs. controls 1336 mL, p=0.002), but also on decreasing transfusion requirements both intra- and postoperatively (cases 544 vs. control 812 mL, p=0.012; cases 193 vs. control 359 mL, p=0.034). They further noted no difference in the Incidence of

thromboembolic event and other complications did not show any differences between TXA and non-TXA groups.(28)

2.3.2 Tranexemic acid in Arthroplasty

In orthopaedics, TXA use has been explored most in field of hip and knee arthroplasty with both topical and intravenous routes of administration used however the most common route remains intravenous. However Topical administration ofTXA at an intra-articular and/or peri-articular soft tissue level is growing in popularity. With one of the advantages of topical use of TXA is the minimal systemic absorption hypothesizing less systemic adverse effects.(23, 29)

In hemi and total hip arthroplasty, most randomized placebo controlled trials clinical trial found that TXA administration safely reduced blood loss (TXA group was 242 mL lower on Postoperative Day (POD) 1 (731 vs. 973 mL, P = 0.01), 294 mL lower on POD 2 (830 vs. 1124 mL, P = 0.0002), and 305 mL lower on POD 3 (902 vs. 1205 mL, P = 0.0005) with a tendency for decreased transfusion rate (cases 17% vs. controls 26%) and total blood product consumption with no significant increase in the risk of thromboembolic event. This showing an 11% decrease in transfusion rates.(4, 12, 30)

In knee arthroplasty, study comparing routes of administration showed all routes had significant reduction of perioperative blood loss and transfusion needs with no superior route of administration.(4) (31)

Study comparing intravenous and topical TXA versus tourniquet showed intravenous TXA use without a tourniquet had less hidden blood loss, a lower ratio of postoperative knee swelling, less postoperative knee pain, lower levels of inflammatory biomarkers, better early knee function, and even better early satisfaction than those treated with a tourniquet.(32)

2.3.3 Tranexemic acid in femoral shaft fractures.

There is a paucity of literature on TXA use in femoral shaft fracture. Two literatures were addressing TXA use in femoral shaft fractures.

90 patient study in India looked at preoperative TXA 10mg/kg in femoral and hip surgeries, looked at postoperative drain volume ($39.33\pm$ as compared to $91.11\pm$ in placebo) 56.8% less than placebo, postoperative heamoglobin on days 0 (2.99 ± 3.457 in the study group as compared to 7.70 ± 6.05 in the placebo a 61.1% difference that has P value 0.01) and 2 (0.3578 ± 0.744 and in

the placebo was 2.7122 ± 2.70 , P value 0.000) a difference of 86.6% Results showed preoperative TXA caused a highly significant reduction in the blood loss in the first 24 hours in patients undergoing surgeries for hip and femoral fractures as well it caused a significant reduction in postoperative anemia and need for transfusion among these patients. In this study out of 45 patients, 18 patients (40%) who fell in the placebo group required blood transfusion and while 7 patients out of 45 (15%) in the study group needed a transfusion ($P=0.01$) a 25% difference in transfusion rates. This study recommended further investigation to determine the effectiveness of TXA in these surgeries.(33)

In Iran, double blinded randomized controlled clinical trial on role of preoperative TXA 15mg/kg versus placebo in intramedullary nailing of proximal femoral fracture shaft was done. With total of 40 patients, each study group was allocated 20 patients. Hemoglobin concentration was used to estimate blood loss, hemoglobin level was measured four hours before and after the surgeries. Blood transfusions observed and integrated into the blood estimation formula. Results showed No significant difference was observed between the groups in drain blood volume four hours after surgery. Mean fall in hemoglobin concentration in placebo group was higher than the TXA group, however, the difference was not statistically significant. ($P= 0.570$) A difference in transfusion rate between the placebo group (30%) and TXA group (5.6%) was also not statistically significant ($P=0.06$) a difference of 25%. Surgeon satisfaction level was also observed and noted to higher in the TXA group (94.4%) compared to the placebo group (80%), however the difference was not statistically significant. The study concluded that intravenous TXA before skin incision in patient undergoing proximal femoral shaft fractures surgery, may reduce intraoperative blood loss and hemoglobin fall however without significant reduction in postoperative anemia. This study recommended further investigations.(34)

CHAPTER THREE

METHODOLOGY

3.1 Study design

This will be an open label single arm trial involving adult patients undergoing open intramedullary femoral shaft nail fixation at Mulago National Referral Hospital.

3.2 Study Site

This study will be carried out in the Orthopaedic Department of Mulago National Referral Hospital.

Mulago National Referral Hospital is located on [name], Kampala, the capital city of Uganda, in Kawempe Division, Mulago Parish. It is about 6 kilometers from city center. It has a bed capacity of about 1500 beds with an annual in-patient turnover in excess of 140,000 patients. It also serves as the teaching hospital for Makerere University, College of Health Sciences.

The Orthopaedic Department of Mulago National Referral Hospital is located in Old Mulago part of the Mulago Hospital Complex, it admits nearly 2000 patients with fractures annually. There are 3 in patient wards including spine ward (manages patients with spine deformities, fractures, infection and tumors), ward 7 (manages closed fractures, musculoskeletal deformities and tumors) and trauma ward (manages closed and open fractures, bone infections, ulcerative tumours) and 3 operating theatres including, spine theatre handles spine surgeries, Ward 7 theatre handles closed fractures, deformities, tumours arthroscopic and arthroplasty surgery, Trauma theatre handles open fractures, bone infections and ulcerative tumor surgery.

The study will be specifically carried out on ward 7, trauma ward and the ward 7 theatre. Patients scheduled for Femoral shaft fracture surgery pre operatively are assessed for their suitability to undergo surgery, Lab tests such as Complete Blood Count to assess hemoglobin levels are done, patients with Hemoglobin levels $\geq 10\text{g/dl}$ are considered fit for surgery other patients are optimized with blood transfusions. All patients preoperatively do have blood Grouping and

Cross matching done before surgery. Intraoperatively, excessive blood loss is prevented, however not always by use of intravenous Tranexemic acid, tourniquet, diathermy, intraoperative hypotension techniques, and occasionally topical / intramuscular adrenaline concoctions. Blood loss intraoperatively is estimated by anaesthesiologist and surgeon who use visual estimation assessing amount of bleeding at surgical site, blood volume in suction drain containers, soaking of the surgical mops, patient's vitals, level of consciousness and mucous membrane pallor. Intraoperatively blood transfusions are sanctioned by anaesthesiologist depending on visual estimation of blood loss, and patient's hemodynamic stability. Postoperatively patients receive intravenous fluids antibiotics, analgesia and are mobilized in and out of bed 12hours. Patients who are clinically aneamic and hemodynamically unstable have a complete blood count done and transfusions sanctioned by attending physician if necessary. DVT investigation and prophylaxis are not routinely done on patients post operatively however at the discretion of the primary surgeon and attending physician for patients at risk this is done.

3.3 Study Population

3.3.1 Target Population

All adult patients with femoral shaft fractures in Mulago National Referral Hospital Orthopaedic Department.

3.3.2 Accessible Population

Adult patients with isolated femoral shaft fractures scheduled for open intramedullary nail fixation at Mulago National Referral Hospital during the study period.

3.4 Study Duration

The study will be conducted over a period of 3 months from the date of ethical approval.

3.5 Selection Criteria

3.5.1 Inclusion Criteria

- . All adult (≥ 18 yrs) patients with isolated closed femoral shaft fractures scheduled for open intramedullary nail fixation in Mulago National Referral Hospital.
- . Patients who will give informed consent to participate in the study

3.5.2 Exclusion Criteria

Patients presenting with

- More than one month after the injury
- Repeat surgery for a fractured femur
- Pathological fractures of the femur
- Undergoing Open Reduction and Internal Fixation of more than one fracture in perioperative period
- Known allergy to Tranexemic Acid
- History of a bleeding disorder
- Medical comorbidities (Diabetes Mellitus, Deep Venous Thrombosis, Pulmonary Thromboembolism)
- Patients already receiving anticoagulants.

3.6 Sample size estimation

3.6.1 Sampling Procedure

Comparison of Two Means (Minn M. Soe and Kevin M. Sullivan, Emory University)

$$n = \frac{(Z_1 + Z_2)^2}{(u_1 - u_2)^2} 2(S)^2$$

$$(u_1 - u_2)^2$$

n = Sample size in each group

Z₁ = 1.96 for 95% confidence level

Z₂ = 0.84 for 80% power

S = Standard Deviation of Outcome in Control Group

u₂ - u₁ = minimum meaningful difference between means

In study done in Mulago by Kajja et al estimated blood loss in 93 patient who underwent open femur shaft fracture intramedullary nailing estimated 72 hours postoperative mean total blood loss at 3.31g/dl, (SD 1.56).

Tranexemic Acid is expected to give 30% reduction in Blood Loss

i.e. $u_1 - u_2 = 0.3$

u₁

$$\underline{3.31 - u_2} = 0.3$$

3.31

$$u_1 - u_2 = 0.993$$

$$n = (1.96 + 0.84)^2 2 \times 1.56^2$$

$$0.993^2$$

$$= 38.7$$

[figure not shown]
$$n = 39$$

$$\text{Adjust for non-response} = 39 / 0.9$$

$$= 43.3 = 43$$

$$N = 43$$

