3.12 Statistical analysis

Data will then be exported into a SPSS version 19 system which will be used for analysis. We will summarise the study population. We will use descriptive statistics such as means (standard deviations) or median and interquartile range (IQR) for continuous variables and proportions for categorized variables. We will also conduct appropriate statistical tests such as chi square or Fischer's test for categorical variables and a one sample independent T-test or wilcoxon sum rank test for continuous variables.

Objective 1: *To determine the effectiveness of pre-operative intravenous Tranexemic acid 15mg/kg on reduction of perioperative blood loss as estimated by difference in 72 hour postoperative and 2 hour preoperative Hemoglobin concentration in patients undergoing open intramedullary nailfixation offemoral shaftfractures in Mulago National Referral Hospital.*

We will assess for the hypothesis that TXA reduces perioperative blood loss by at least 30% using one sample independent T-test

Objective 2: *To determine effectiveness of pre-operative intravenous Tranexemic acid 15mg/kg on reduction of transfusion rates by 30% inpatients undergoing open intramedullary nail fixation offemoral shaftfractures in Mulago National Referral Hospital.*

We will conduct univariate analysis and adjust for effect modification and confounding.

Objective 3: *To determine the safety of pre-operative intravenous Tranexemic acid 15mg/kg in patients undergoing open intramedullary nailfixation offemoral shaftfractures in Mulago National Referral Hospital.*

We will assess for safety using descriptive statistics showing proportions of adverse events in the study group.

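### The 80% power in section 3.6 comes from a two-group formula, but the trial has one arm and a one-sample test; the power of the actual design is not stated and depends on a null value that is not fixed

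*Combined protocol and SAP*

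**What the plan says.** Section 3.6.1 of the combined protocol and SAP names its method as "Comparison of Two Means". The formula carries a factor of 2 on the variance. It defines "n = Sample size in each group" and takes S as "Standard Deviation of Outcome in Control Group". The error rates enter as "1.96 for 95% confidence level" and "0.84 for 80% power". The reference values come from an earlier series of 93 patients at the same hospital, which "estimated 72 hours postoperative mean total blood loss at 3.31g/dl, (SD 1.56"). A 30% reduction is expected, that is 0.993 g/dl. The result is 38.7, taken as 39, and then 43 after 10% non-response. The figure is not doubled for a second group.

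Section 3.1 states: "This will be an open label single arm trial". Section 3.12 says that the primary hypothesis, a reduction of 30% or more, will be assessed "using one sample independent T-test". It gives no null value in g/dl. No power calculation for a one-sample test appears anywhere. The data collection sheet (Appendix II) still has a field for study arm A or B.

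**The concern.** The factor 2 in the formula allows for sampling error in two means, each estimated from a group of n patients. This trial enrols one group, and the named test compares its mean with a fixed number. The stated 80% therefore belongs to a comparison of 39 with 39 (78 evaluable patients), which will not be made.

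Two further matters follow once the design is taken as written. First, the fixed number is itself an estimate from 93 patients, and a one-sample test ignores its error. Second, section 3.12 does not say whether the test value is 3.31 g/dl or the 30%-reduced mean. The power differs greatly between the two. At stake is whether the sample size justification for the primary outcome says what the trial can show.

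**Working it through.** **Inputs.** All are from section 3.6.1 unless noted: reference mean 3.31 g/dl, SD 1.56, historical n = 93, planning reduction 30%, z-values 1.96 and 0.84, 39 evaluable and 43 enrolled. The two-sided 5% level is implied by 1.96; sidedness is not stated in words. Assumption: the SD under treatment equals the historical 1.56, except where varied in step 6.

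**1. The plan's own figure.**
- Difference = 0.3 × 3.31 = 0.993.
- n = (1.96 + 0.84)² × 2 × 1.56² / 0.993² = 38.7, so 39 per group.
- 39 / 0.9 = 43.3, given as 43.

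The arithmetic reproduces. Power for 39 against 39 is 80.3% (normal approximation).

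**2. Same inputs, one-sample form.**
- n = (1.96 + 0.84)² × 1.56² / 0.993² = 19.35.
- With the noncentral t distribution, power is 79.2% at n = 21 and 81.2% at n = 22.

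**3. Planned size, null 3.31 treated as known.** The standard error at n = 39 is 1.56/√39 = 0.250, so the noncentrality is 0.993/0.250 = 3.98. Exact t power is 97.2% at 39 and 98.3% at 43. The smallest reduction detectable with 80% power is 21.7% at 39 (0.72 g/dl) and 20.6% at 43.

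**4. Planned size, error of the 93-patient mean counted.** The standard error is 1.56 × √(1/39 + 1/93) = 0.298, so the noncentrality is 0.993/0.298 = 3.34. Two-sample t power is 91.2% at 39 and 92.9% at 43. The smallest reduction detectable with 80% power is 25.4% at 39 and 24.5% at 43.

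*Type I error if that error is ignored.* The one-sample test uses 0.250 where the real standard error is 0.298. The critical value 1.96 then acts as 1.96 × 0.250/0.298 ≈ 1.645, and the two-sided error is about 10% at n = 39 instead of 5%.

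**5. Null taken as the 30%-reduced mean.** The null value is 3.31 − 0.993 = 2.317 g/dl. One-sample t-test, n = 39, power to show a larger reduction:

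| True reduction | Distance from null (g/dl) | Power |
|---|---|---|
| 30% | 0 | 2.5% |
| 40% | 0.331 | 25% |
| 50% | 0.662 | 73% |

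**6. SD range (assumed values).** One-sample t-test against 3.31, n = 39, difference 0.993:

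| SD | Power |
|---|---|
| 1.2 | 99.9% |
| 1.56 | 97.2% |
| 2.0 | 85.6% |
| 2.5 | 67.6% |

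**The case against.** The strongest reply is that no harm is done. Against 3.31 g/dl the formula overstates the need, so the trial has more than the power it claims, and no patient would be added or removed. Section 3.6.1 also states the effect, SD, confidence level and power openly. Its comparator is itself a sample, so allowing for error in two means is not unreasonable. Against 93 historical patients, about 25 treated patients would already give 80% power by a two-sample t-test.

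Much of this stands, and it is why the severity is moderate. It does not rescue the stated figure. The formula assumes a second group of 39, not a historical group of 93, and section 3.12 plans neither comparison. The reassurance also holds only if the null is 3.31, which section 3.12 does not say.

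A reader might infer that half the sample is missing and that 78 patients are needed. The documents do not support that: one arm is planned, and 39 evaluable patients exceed what a test against 3.31 requires. A reader might also infer that a randomised control group was intended and dropped. Section 3.6.1 speaks of a control group but never of randomisation, and it takes the control values from the historical series. The arm field in Appendix II is compatible with a leftover from a two-arm plan but does not establish one.

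**Conclusion.** The point holds as a mismatch between the sample size calculation and the design. The stated 80% is not the power of this trial at the planning effect under any reading of the one-sample test.

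- **Null 3.31 g/dl:** the error is conservative. Power with 39 evaluable patients is about 97% with 3.31 treated as fixed, or about 91% with its sampling error counted. The first option carries a real type I error of about 10%.
- **Null 2.317 g/dl:** the trial has almost no power at the planning effect.

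These figures assume a two-sided 5% level, a final analysis without interim adjustment, and an SD of 1.56 under treatment. The documents do not support that SD for treated patients. They also assume that the historical and new patients differ only by treatment and chance.

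It would be tempting to conclude that the trial is underpowered, or that it should be cut to about 22 patients. Neither follows. The first is wrong for a null of 3.31. The second ignores the error of the historical mean and the uncertainty in the SD. Severity is moderate, since enrolment does not change under the 3.31 null.

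**What to change.** Keep N = 43 and make these changes:

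1. In section 3.6.1, remove the two-group formula and the definition of n as a per-group size.
2. In both 3.6 and 3.12, state that the null is no reduction from 3.31 g/dl, that 30% is the planning effect and not the null, and that the test is two-sided at 5%.
3. Name one test and give its matching power.
   - *Preferred:* a comparison with the historical mean that carries its error (3.31, SD 1.56, n = 93). With 39 evaluable patients this has about 91% power for 0.993 g/dl and 80% power for a reduction of about 25%. Section 3.12 must be amended to that test.
   - *If the one-sample t-test is kept:* state about 97% power, and say plainly that 3.31 is treated as known without error.
4. Give an SD range, labelled as an assumption. For the one-sample test at n = 39, the values in step 6 of the working can be used. For the preferred comparison, the range should be recomputed.

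The cost is a rewritten section 3.6 and a few sentences in 3.12. Enrolment and data collection do not change.

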3.6.2 Allocation of intervention

3.7 Study Procedure

3.7.1 Participant recruitment

Participants who meet criteria for inclusion and exclusion will be recruited from two wards i.e. ward 7 and Trauma ward. Principle investigator and research assistant shall access patient's file and use screening tool to assess patient's eligibility for enrollment into the study. If patient is eligible participants will be educated on the study procedure and informed consent will be achieved. Participants will be clinically assessed for the Risk of thromboembolic events and have hematological screening for thromboembolic events or bleeding dyscrasias with Prothrombin Time and International Normalized Ratio (PT-INR) and activated Partial Thromboplastin Time (aPTT) done prior to enrollment. Pre tested data collection tool will then be used by the principal investigator and his research assistants to collect participants demographics and clinical data.

3.7.2 Blood collection Procedure for hemoglobin Estimation.

The principal investigator or his research assistants will draw 2.0 mls of blood under aseptic conditions from the cubital vein of the participant, using a Becton Dickinson vacutainer® system containing EDTA-K3. The tube will be shaken to allow proper mixing of blood with the anticoagulant, legibly labeled with first and given name, age, sex and hospital number of the patient. A laboratory request form for hemoglobin determination will be filled by principal investigator or his research assistants and both the sample and the form delivered to the hospital central laboratory. Upon receiving the result the Hemoglobin concentration will be entered into the data collection tool as Preoperative Hemoglobin in g/dl.

Blood for hemoglobin concentration estimation will be collected 2 hours prior to surgery and 72 hours after surgery. Optimal timing for post-operative haemoglobin concentration monitoring still remains a challenge, however studies in orthopaedic surgeries have noted major variation in hemoglobin concentration estimations from day 0 to day 2 which is attributed to hemodilution with colloids and crystalloids together with ongoing hidden blood losses into the joint cavity and within soft tissue planes. From day 3 onwards minimal changes are noted and this is attributed to haemostabilisation. (35-37)

3.7.3 Tranexemic Acid other preoperative drugs.

Tranexemic Acid (Kapron, Egypt) 500mg / 5ml ampoule will be used. Drug will be prepared at 15mg/kg by the anaesthetist who will administer it for over 10mins to prevent drug induced hypotension, dizziness vomiting and nausea. 10mins before skin incision so as to achieve optimal plasma and interstitial concentrations.

All patients will receive pre-operative antibiotics, before the surgery.

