2.2 Tranexemic Acid

Okamoto et al discovered trans-4-Aminomethyl-Cyclohexanecarboxylic Acid (Tranexamic acid) as a potent antifibrinolytic superior to the previously used antifibrinolytic lysine analogue Epsilon-Aminocaproic Acid (EMCA).(22) TXA is an Antifibrinolytic Agent. TXA is a synthetic derivative of the amino acid lysine with antifibrinolytic activity. With strong affinity for the five lysine-binding sites of plasminogen, TXA competitively inhibits the activation of plasminogen to plasmin, resulting in inhibition of fibrinolysis ensuring stabilization of clot: at higher concentrations, this agent noncompetitively inhibits plasmin. This agent has a longer half-life, is approximately ten times more potent, and is less toxic than aminocaproic acid, which possesses similar mechanisms of action.(10)

Tranexemic acid has two formulations i.e. Oral tablet and injectable solution, however in surgery Injectable solutions have been mostly used due to the rapid distribution in intracellular and extracellular compartments. Despite several clinical studies proving the efficacy of TXA with single or multiple boluses of different sizes with or without subsequent infusions, no consensus has been reached regarding the optimal regimen for intravenous TXA administration. Previous studies have established the need for a therapeutic plasma concentration of 10 ng/ mL and an 80% reduction in the activity of plasminogen activator for adequate suppression of fibrinolysis in

tissues, the dosage of 10-15mg/kg has been found to achieve this concentration within 10 mins of administration in the knee Arthroplasty surgeries. (23) (24) (25)

TXA has been reported to be a safe drug with a large therapeutic window and adverse effects mostly documented at high doses >20mg/kg. Some of the common adverse effects of intravenous TXA reported are.

- Hypotension, this is associated with rapid infusion, infusion rate of at most 1 mL per minute is recommended.
- Gastrointestinal disturbances (nausea, vomiting, diarrhea)
- Allergic dermatitis, giddiness
- The risk of thromboembolism among patients receiving TXA has been shown not to be different from those not receiving TXA (10, 23, 26)

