3.7.4 Surgical Time

Time of skin incision and last skin suture will be documented to determine surgical time. It will be presented in minutes.

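### Section 3.7.3 limits infusion speed only by a fixed time, so an undiluted 10-minute dose exceeds the 1 mL/min of section 2.2 above 66.7 kg (minor; state rate, concentration and timing together)

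*Combined protocol and SAP*

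**What the plan says.** The operative instruction is in section 3.7.3. For the product: "500mg / 5ml ampoule will be used". For dose, speed and purpose: "Drug will be prepared at 15mg/kg by the anaesthetist who will administer it for over 10mins to prevent drug induced hypotension". For timing: "10mins before skin incision so as to achieve optimal plasma and interstitial concentrations". The section gives no mL/min or mg/min limit, no dilution, no maximum dose and no duration that depends on weight. The eligibility criteria (3.5.1, 3.5.2) and the screening tool (Appendix I) set no weight limit.

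The only infusion rate anywhere in the document is in section 2.2, in the literature review's list of reported adverse effects: "Hypotension, this is associated with rapid infusion, infusion rate of at most 1 mL per minute is recommended". No concentration is attached to it. The same section says of the drug generally: "adverse effects mostly documented at high doses >20mg/kg".

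Hypotension is a listed safety outcome (3.8.2). The data collection sheet (Appendix II) has a field for weight and a place to record hypotension before or during surgery. Section 3.7.4 adds: "Time of skin incision and last skin suture will be documented to determine surgical time". The sheet has no field for dose given, concentration, or infusion start and stop times.

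**The concern.** Section 3.7.3 slows the infusion in order to prevent hypotension. With a fixed time and a dose proportional to weight, however, the heaviest patients receive the drug fastest. An anaesthetist can follow the time rule exactly and still exceed the only rate the document recommends for the harm that the rule is meant to prevent.

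Two things are at stake. The first is a dosing instruction that does not secure its own stated purpose across the weights the trial admits. The second is interpretation. Safety is defined in 3.8.2 as events secondary to the drug, and the trial has one arm. If hypotension occurs, the rate at which that patient was infused would be a natural thing to check. Weight gives the intended dose, but the sheet does not allow the actual rate to be reconstructed.

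**Working it through.** The plan gives no infusion rate for the study dose and no weight threshold, so there is no plan figure to reproduce. The 1 mL/min is a reported recommendation.

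**Inputs**
- Dose: 15 mg/kg, no maximum (3.7.3).
- Strength: 500 mg / 5 mL = 100 mg/mL (3.7.3).
- Time: 10 minutes (3.7.3). The wording can mean longer than 10 minutes (a floor) or across 10 minutes.
- Reference rate: 1 mL/min (2.2), concentration not given.
- Assumptions: drug undiluted; 1 mL/min refers to the ampoule strength, that is 100 mg/min.

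**Formulas**
- Volume = 15 × weight / 100 = 0.15 mL per kg.
- Rate over 10 minutes = 0.15 × weight / 10 = 0.015 mL/min per kg.
- Threshold weight at 1 mL/min = 10 min × 100 mg/min / 15 mg/kg = 66.7 kg.
- Shortest time that respects 1 mL/min = 0.15 min per kg, with a floor of 10 minutes.

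| Weight (kg) | Dose (mg) | Volume (mL) | Rate in 10 min (mL/min) | Time needed at 1 mL/min (min) | Extra over 10 min |
|---|---|---|---|---|---|
| 60 | 900 | 9.0 | 0.90 | 9.0 (floor 10) | 0 |
| 66.7 | 1000 | 10.0 | 1.00 | 10.0 | 0 |
| 70 | 1050 | 10.5 | 1.05 | 10.5 | 0.5 |
| 80 | 1200 | 12.0 | 1.20 | 12.0 | 2 |
| 90 | 1350 | 13.5 | 1.35 | 13.5 | 3.5 |
| 100 | 1500 | 15.0 | 1.50 | 15.0 | 5 |

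**Sensitivity to the assumptions**
- Duration, with a limit of 100 mg/min: threshold = minutes × 100 / 15, giving 66.7 kg at 10 minutes, 80 kg at 12 and 100 kg at 15.
- Concentration behind the 1 mL/min, at 10 minutes: 50 mg/mL gives 10 × 50 / 15 = 33.3 kg; 200 mg/mL gives 10 × 200 / 15 = 133.3 kg.
- Dilution, if 1 mL/min is a plain volume rate: at 50 mg/mL the volume is 15 / 50 = 0.30 mL per kg, and 10 mL / 0.30 = 33.3 kg. On that reading a cap of 100 mg/min would run at 100 / 50 = 2 mL/min, twice the limit. A mg/min cap alone therefore does not settle the matter unless the concentration is fixed with it.

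**The case against.** The strongest reply is that the benchmark is not a trial rule. The 1 mL/min figure is background text without a concentration, while the operative section already addresses hypotension by means of a duration and puts an anaesthetist in charge. That stands: the gap lies between a literature review and a procedure, and the protocol does not contain two conflicting instructions.

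The 66.7 kg figure is also conditional. Varying only the concentration behind the 1 mL/min moves the threshold from 33.3 to 133.3 kg, and no weight distribution is given, so the share of patients affected cannot be calculated. That stands too, but 100 mg/mL is the only product strength in the document.

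Harm is not shown. The excess is 5% at 70 kg and 20% at 80 kg on the stated assumptions, and section 2.2 places most adverse effects above 20 mg/kg, against 15 mg/kg here. That last statement concerns total dose, whereas the hypotension item concerns speed, so it softens the point without removing it. Hypotension is also looked for, and the monitoring board can stop the trial for safety.

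A reader might infer more than the documents support:
- That the plan requires too fast an infusion in heavier patients. It does not: the time can be read as a minimum, the anaesthetist may go slower, and dilution is left open.
- That heavier patients face a demonstrated hazard. Nothing in the documents ties an excess of this size to hypotension.
- That the efficacy result is compromised. Hypotension is one of several transfusion criteria in Appendix III and does not trigger transfusion there alone. The documents give no basis for carrying a rate effect through to the primary outcome or its test.

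**Conclusion.** The point holds as a minor one. Section 3.7.3 controls speed by a fixed time for an uncapped weight-based dose. Given undiluted in 10 minutes, and with 1 mL/min read at the ampoule strength, the dose exceeds the section 2.2 recommendation in anyone above 66.7 kg, by 20% at 80 kg and 50% at 100 kg. The plan permits this rather than requires it.

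The conclusion rests on three conditions: undiluted drug, a 10-minute infusion, and 100 mg/mL as the concentration behind the 1 mL/min. The added risk is unquantified and probably small, the proportion of patients concerned is unknown, and the sample size and primary analysis are untouched. It is worth acting on because the remedy is short and makes the instruction serve the purpose it already states.

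**What to change.** In section 3.7.3, write in substance:

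> The drug is given undiluted (100 mg/mL) at no more than 1 mL/min (100 mg/min), over at least 10 minutes or 0.15 minutes per kg, whichever is longer, and the infusion is completed before skin incision.

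State in the same place whether the 10 minutes before incision (also shown in the section 1.7 framework) is the start or the end of the infusion. Rate and timing have to be settled together:
- If it is the start, a 10-minute infusion already ends at incision. Patients above 66.7 kg then need an explicit allowance to start earlier, for example 15 minutes before incision at 100 kg. Without it, the cap would breach either the start time or the requirement to finish before incision.
- If it is the end, the infusion starts 10 + 10 = 20 minutes before incision up to 66.7 kg, and 10 + 15 = 25 minutes before at 100 kg.

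If the sponsor prefers to dilute, state the concentration and the matching mL/min and mg/min limits.

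Optionally, add dose given, concentration, and infusion start and stop times to Appendix II, so that the actual rate behind any hypotension event can be worked out.

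Cost: the rate cap adds 0 minutes up to 66.7 kg, 0.5 at 70 kg, 2 at 80 kg, 3.5 at 90 kg and 5 at 100 kg, so the infusion starts slightly earlier relative to incision in heavier patients. Sample size, endpoints and analysis do not change.
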